Belimumab and placebo will be supplied as open-label vials and 3rd party unblinding will be employed. The study agent will be reconstituted and diluted by the unblinded site pharmacist or designee, independent of the study (person responsible for receiving and dispensing study agent). Separate monitors will be responsible for the clinical (blinded monitor) and study agent (unblinded monitor) aspects of the study.

If a medical emergency occurs and a decision regarding the subject's condition requires knowledge of the treatment assignment, the study blind may be broken for the specific subject. Whenever possible, the investigator should consult with the principal investigator of the study and data safety monitoring board prior to unblinding any subject. Any broken blind will be clearly justified and explained. The lead site and sponsor must be notified of any broken blind regardless of whether it was done for emergency or non-emergency reasons.

e. Concurrent Medications:

Corticosteroids: Patients that are on glucocorticoids at the time of screening will be required to be on a stable background dose for at least 2 weeks prior to screening (prednisone (or equivalent) dose \leq 15 mg daily).

The prednisone dose will remain stable until week 24 of the study, at which time a taper will be allowed at the discretion of the site investigator and principal investigator.

An increase in the dose of oral prednisone will be permitted, if clinically necessary, during the first 8 weeks after randomization without accounting it as a disease flare. In this case, the dose of prednisone must be tapered (to less than or equal to 25% of the baseline dose) by week 12. However, if the dose of prednisone cannot be tapered by week 12, the event will be considered as disease flare at that time.

Any increase of the prednisone dose after week 8 for IIM disease activity or the use of pulse steroids at any time during the study will be considered a disease flare. An increase of the prednisone dose at any time during the study for an event other than worsening of IIM disease activity will require the patient to return to the baseline dose of prednisone within 10 days, without accounting the event as a disease flare. Patients that are considered treatment failures will be allowed to remain in the study, in respective groups, at the discretion of the treating physician and PI.

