3. an increased dose of corticosteroid before study week 8 and did not return to $<25\%$ above the baseline dose by week 12.

Endpoints:

1. **Primary Endpoint:**
 - a. Response rate at 40 weeks defined as percentage of patients meeting definition of improvement (DOI) in IIM patients treated with belimumab and standard therapy compared to the percentage of patients meeting DOI treated with placebo and standard therapy.
2. **Secondary Endpoints:**
 - a) Incidence of flares: flare rates during 40 weeks randomization period in patients with IIM treated with belimumab and patients treated with placebo and at week 64 in each group.
 - b) Time to achieve initial improvement defined as the time to reaching DOI.
 - c) Duration of improvement; quantified as the time from achieving improvement to the time of worsening or a disease flare. (Time from 1st DOI to 1st DOW or disease flare event). This will be based on the subset of subjects who achieve improvement.
 - d) Percent change in muscle enzyme levels (CPK and myoglobin) from baseline to week 40 and 64 in each respective group
 1. $<20\%$ reduction: no response
 2. 20-70% reduction: partial response
 3. $>70\%$ reduction: complete response
 - e) Percent change in manual muscle assessment (MMT-8) from baseline to week 40 and week 64 in each respective group.

- 1. <20% reduction: no response
- 2. 20-70% reduction: partial response
- 3. >70% reduction: complete response
- f) Percent change in prednisone dose from baseline to week 40 and week 64 in each respective group
- g) Proportion of subjects, among those on steroids at baseline, able to reduce the prednisone dose to ≤ 5 mg daily at week 40 and week 64 in each respective group.
- h) Flare rate in placebo group during the 40 week randomized treatment phase as compared to that group in the 20 week open label phase.
- i) Serious adverse event and adverse event rates
- j) Changes in B cell populations from baseline to week 40 and week 64
- k) Changes in autoantibody titers from baseline to week 40 and week 64
- l) Changes in immunoglobulin concentrations from baseline to week 40 and week 64

Inclusion Criteria:

Subjects enrolled in the study must meet the following inclusion criteria:

- 1) Adults ≥ 18 years of age
- 2) Have a diagnosis of:
 - a. definite or probable dermatomyositis (DM) by modified Bohan & Peter criteria or

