 - b. Definite or probable diagnosis of polymyositis (PM) with presence of one of myositis specific antibodies. In the absence of myositis specific auto-antibodies, the diagnosis of PM will require review of the muscle biopsy and adjudication by the predetermined committee of experts.
- 3) Presence of positive autoantibody (ANA $\geq 1:80$ or RNP or SSA/SSB or any of the myositis specific autoantibody anti-synthetase autoantibodies (anti-Jo-1, PL-7, PL-12, EJ, OJ), anti-SRP, anti-Mi-2, anti-p140 [also known as anti-MDA5], anti-p155/140 [also known as anti-TIF], anti-NXP-2 [also known as MJ]).
- 4) Have refractory IIM as defined by inadequate response or intolerance to at least 3 months of glucocorticoids and/or an inadequate response or intolerance to at least 3 months at least one other immunosuppressive agent, such as azathioprine, methotrexate, IVIG, mycophenolate mofetil, leflunomide, tacrolimus, cyclosporine cyclophosphamide, and Rituximab.
- 5) Have active IIM at screening. This requires at least 3 criteria from the CSM (listed above) to be met for enrollment.
- 6) Dermatomyositis patients that do not meet the MMT criteria, must have:
 - a. a cutaneous VAS score of >3 cm on a 10 cm VAS scale (MDAAT) will be required:
 - b. elevation of at least one muscle enzyme (creatinine kinase [CK]; myoglobin; alanine aminotransferase [ALT]; or aspartate aminotransferase [AST]) to a minimum level of 1.3 times the upper limit of normal,
 - c. and 1 additional core set measure
- 7) For patients with ≥ 7 years of IIM, muscle biopsy or muscle MRI within 4 months prior to enrollment will be required to document active myositis to avoid enrolling patients with significant index of damage/ muscle atrophy. This is not applicable to DM patients with a cutaneous VAS score of >3 cm on a 10 cm VAS scale (MDAAT).
- 8) Have a stable background glucocorticoid therapy for at least 2 weeks prior to screening

(Prednisone (or equivalent) dose \leq 15 mg daily)

9) Immunosuppressive therapy (IS) at the time of enrollment is not required. However, a patient receiving IS therapy at the time of enrollment must be on a stable regimen (azathioprine, mycophenolate mofetil, tacrolimus, cyclosporine for \geq 2 months prior to screening. Patients on intravenous gamma globulin (IVIG) have to be on a stable dose and frequency regimen for \geq 3 months.

Therapeutic Agent	Treatment Duration prior to Screening \geq	Dose Increase prior to Screening \geq
Azathioprine	2 months	2 weeks

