The Biostatistics Randomization Management System (BRMS) is a secure, HIPAA-compliant, web-based application that allows investigators to randomize subjects into randomized clinical trials (RCTs) using their personal computer. The BRMS allows for multi-center, stratified, and single/double blinded RCTs, using permuted blocks. Randomization notifications are automatically sent to the PI and other authorized personnel. Using BRMS is a good way to maintain compliance in RCTs.

Statistical Considerations

SPECIFIC STATISTICAL AIMS

The primary objective of the study is to compare subjects in the Belimumab group and subjects in the placebo group with respect to response (improvement) at week 40.

The specific aims of the study are to compare the two treatment arms (Belimumab vs. Placebo [P vs. B]), during the 40-week randomized phase of the study, with respect to the following:

1. Response at week 40.
2. Flare rates during the 40-week treatment period.
3. Time-to-achieve (initial) improvement during the 40-week randomized phase of the study
4. Duration of improvement during the 40-week randomized phase of the study, among those who achieved improvement (this is essentially a time-to-flare/relapse analysis from the time that you achieved improvement)
5. Change in muscle enzyme levels (CPK, myoglobin) from baseline to week 40
6. Change in MMT-8 from baseline to week 40
7. Change in prednisone dose from baseline to week 40

8. Proportion of subjects able to reduce prednisone dose to ≤ 5 mg at week 40
9. Change in B cell populations, immunoglobulin levels and BLys levels from baseline to week 40.
10. Change in autoantibody titers from baseline to week 40.
11. Rates of SAEs and AEs experienced

STATISTICAL METHODS

All subjects will be analyzed according to the intention-to-treat [ITT] principle. A subject will be considered evaluable and will be included in the intention-to-treat analysis if he/she received at least the first five of the planned infusions during the randomized phase of the study. Subjects who do not get the first five infusions will be considered ‘drop-outs’. It should be noted that the study protocol calls for patients remaining on their treatment assignment. However, adjustments in dosages of medications used in their ‘standard care’ are permitted during the first 8 weeks. Analyses that take into account the actual treatment received (e.g. accounting for compliance, etc.) will be carried out as a secondary analysis (per protocol [PP] analysis).

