treatment and time (baseline vs. week 40; or all available data at each study visit) or other factors of interest will be examined (e.g. Treatment X Disease Type; Treatment X Disease Severity). The treatment-by-time interaction term, will demonstrate whether the trajectories (or patterns of change) in the outcomes of interest are different between treatment groups. Data transformations may be used, in order to meet the necessary assumptions for the mixed models analyses. If transformations do not achieve the assumptions needed, a rank transformation or an appropriate non-parametric method will be considered.

If the analysis using a mixed model approach is not feasible due to the pattern of the data, then, a simplified analysis comparing the two treatment arms with respect to percent change (reductions) in muscle enzymes, MMT-8 and prednisone dose will be carried out using either a t-test or the Mann-Whitney test, as appropriate. A chi-square test or Fisher's exact test, as appropriate, may also be used if the continuous measures are grouped according to pre-specified categories (e.g. reduction in CPK will be categorized as No Response, Partial Response or Complete Response according to whether the percent reduction was <20% vs. 20%-70% vs. >70%, respectively).

6. For specific aim 8, the proportion of subjects who were able to reduce their daily prednisone dose to ≤ 5 mg at week 40, will be compared using either a chi-square test or Fisher's exact test, as appropriate.
7. For specific aim 11, either a chi-square test or Fisher's exact test, as appropriate, will be conducted to compare the proportion of subjects who experienced any SAEs or AEs during the randomized phase of the study. For this analysis, each subject will be categorized at the end of 40 weeks as having had any SAEs/AEs or not having any SAEs/AEs.

Multivariable analyses (logistic, cox) will be conducted for the above outcomes, if feasible. However, this may be limited by the sample size.

SAFETY DATA

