From available trials in IIM, there is an observed placebo effect of 0%-40% at 12 weeks^{9,10} and 0% at 52 weeks⁹. These results demonstrate that the placebo response rate at 40 weeks can be very variable. One clinical study looking at rituximab in myositis was the first prospective, double-blind, randomized trial in myositis and the largest clinical trial ever performed in the inflammatory myopathies¹⁶. This trial employed a unique design; subjects were divided into two groups: early-start and delayed-start of rituximab. Overall, 83% of enrolled subjects (with severe refractory disease) met the DOI by the end of the trial, despite lack of statistical significance between groups. An alternate double-blind, placebo-controlled trial of etanercept (50 mg subcutaneously weekly for 52 weeks) where 16 subjects were randomized showed that: all 5 subjects receiving placebo were treatment failures (median time to treatment failure: 148 days)¹⁷. In contrast, 5 of 11 subjects in the etanercept arm were successfully weaned off prednisone; the median time to treatment failure in this group was 358 days ($p = 0.0002$). This data shows that for myositis trials, placebo response is often close to 0%. In order to achieve a clinically meaningful difference between study treatment arms, the response rate of the treatment group would need to be at least 50%.

We hypothesize (optimistically) the response rate at 40 weeks in the placebo arm to be 5%. We further assume that a magnitude of difference of 45% would be clinically meaningful (this corresponds to a 50% response rate in the Belimumab arm).

Based on the assumption that a difference of 45% in response rates at 40 weeks between Placebo and the investigational agent, Belimumab, would be clinically meaningful, then, a two group chi-square test ($\alpha=0.05$, two sided test) will yield 80% power to detect a difference between the Placebo arm week 40 response rate of 5% and a Belimumab-treated arm week 40 response rate of 50% (Odds ratio=19) when the sample size in each group is 15, assuming the dropout rate is 0%.

Table 1 below shows the sample size requirements for various pairs of (hypothesized) 40-week response rates and assumptions on what would be a clinically meaningful difference between treatment arms. Corresponding sample sizes are provided for the specified range of parameters. Calculations were based on a two-sided chi-square test to achieve 80% power ($\alpha=0.05$).

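### The prednisone 5 mg endpoint has two different denominators, and no version says how patients already at or below 5 mg at baseline are handled

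*Combined protocol and SAP*

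**What the plan says.** The endpoint appears three times in the combined protocol and SAP.

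- **Endpoints, secondary endpoint g:** "Proportion of subjects, among those on steroids at baseline, able to reduce the prednisone dose to" 5 mg daily or less, at weeks 40 and 64. The denominator is baseline steroid users.
- **Specific Statistical Aims, aim 8:** "Proportion of subjects able to reduce prednisone dose to" 5 mg or less at week 40. No restriction is given.
- **Statistical Methods, item 6:** the arms are compared on "the proportion of subjects who were able to reduce their daily prednisone dose to" 5 mg or less at week 40, by chi-square or Fisher's exact test. Again no restriction is given.

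The analysis set does not supply one. A patient is evaluable if "he/she received at least the first five of the planned infusions during the randomized phase of the study", with no steroid condition.

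On steroid use at entry, two sections differ. Concurrent Medications is conditional: "Patients that are on glucocorticoids at the time of screening will be required to be on a stable background dose". Inclusion criterion 8 reads as though every patient is a user: "Have a stable background glucocorticoid therapy for at least 2 weeks prior to screening". Both cap the dose at 15 mg daily and neither sets a minimum. After entry, "The prednisone dose will remain stable until week 24 of the study", and tapering is then allowed at discretion.

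Endpoint f is the percent change in prednisone dose. The planned analysis of aim 7 (change in dose) is a repeated-measures mixed model. Percent change returns in Statistical Methods as the fallback if that model cannot be fitted.

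**The concern.** A patient who enters at 5 mg or less cannot move from above the threshold to below it. That patient carries no information on whether belimumab allows steroids to be reduced to that level, yet stays in the denominator under every version of the endpoint. Under aim 8 and item 6, so does any patient who takes no prednisone at all.

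Two things are at stake. The first is the size of the estimated effect: patients who cannot make the transition pull the two arm proportions together. The second is pre-specification. With two denominators and no scoring rule, the choice may be made after the doses have been seen, and in a trial of 30 patients that choice can change the result visibly.

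**Working it through.** **The plan's own figure.** The only sample size given is for the primary endpoint: 5% v 50%, two-sided α = 0.05, 80% power. With p̄ = 0.275,

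n = [1.96 × √(2 × 0.275 × 0.725) + 0.842 × √(0.05 × 0.95 + 0.50 × 0.50)]² / 0.45² = (1.238 + 0.459)² / 0.2025 ≈ 14.2, rounded up to 15 per arm.

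This matches the plan. No power is stated for the prednisone endpoint, so nothing below changes the trial's N.

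**Dilution.** Let f be the share of each arm at or below 5 mg at baseline (including non-users, if they enter). Let p_B and p_P be the true rates among patients starting above 5 mg, with D = p_B − p_P. Assume f is the same in both arms and all such patients are scored the same way.

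- Scored as successes: [f + (1 − f)p_B] − [f + (1 − f)p_P] = (1 − f)D
- Scored as failures: (1 − f)p_B − (1 − f)p_P = (1 − f)D

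The shrinkage is the same under both scorings. Only the level of the rates differs.

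**Illustration.** The documents give neither f nor rates for this endpoint. Assume 20% v 50% among patients starting above 5 mg (D = 30 points).

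| f | scored as successes | scored as failures | difference |
|---|---|---|---|
| 0 | 20% v 50% | 20% v 50% | 30 points |
| 20% | 36% v 60% | 16% v 40% | 24 points |
| 33% | 47% v 67% | 13% v 33% | 20 points |
| 50% | 60% v 75% | 10% v 25% | 15 points |

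**Does restriction cost more than it gains?** Approximate chi-square power is Φ[(difference − 1.96 × SE₀)/SE₁], where SE₀ = √(2p̄(1 − p̄)/n) and SE₁ = √([p_P(1 − p_P) + p_B(1 − p_B)]/n). For example, at 36% v 60% with n = 15: SE₀ = √(2 × 0.48 × 0.52/15) = 0.182, SE₁ = √((0.2304 + 0.24)/15) = 0.177, and power = Φ[(0.24 − 0.358)/0.177] = 0.25. Unrestricted rows use 15 per arm. Restricted rows use 12, 10 and 8 per arm (the last is 7.5 rounded up). The second block borrows the primary endpoint's 5% v 50% as a more favourable case.

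| assumed rates above 5 mg | handling | f = 20% | f = 33% | f = 50% |
|---|---|---|---|---|
| 20% v 50% (0.40 at f = 0) | kept as successes | 0.25 | 0.19 | 0.14 |
| | kept as failures | 0.30 | 0.25 | 0.19 |
| | restricted | 0.33 | 0.28 | 0.23 |
| 5% v 50% (0.82 at f = 0) | kept as successes | 0.52 | 0.37 | 0.24 |
| | kept as failures | 0.68 | 0.57 | 0.43 |
| | restricted | 0.72 | 0.63 | 0.53 |

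Fisher's exact test at 5% v 50% gives the same ordering: restricted 0.59, 0.43, 0.28; successes 0.35, 0.23, 0.13; failures 0.57, 0.42, 0.23. Against scoring as failures, the gain at f = 20% and 33% is slight.

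**Equal f.** Randomization is not stratified by prednisone dose. At f = 33% and 15 per arm, the between-arm difference in that share has standard deviation √(2 × 0.333 × 0.667/15) = 0.17. If these patients were scored as successes, such an imbalance would enter the estimate directly.

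**The case against.** A reader might infer that the plan counts patients already at 5 mg or less as automatic successes. The documents do not say so. All three versions speak of being able to reduce the dose, and read literally a patient who enters at 5 mg and stays there has reduced nothing. The scoring is undefined, not defined wrongly. This answers the stronger reading but not the point, because dilution follows under either scoring if these patients remain in the denominator.

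It can also be said that item 6 is shorthand for endpoint g and presupposes that the patient takes prednisone. If inclusion criterion 8 governs entry, every patient is a user and the omitted restriction changes nothing. That is fair, and it is why the two entry statements must be reconciled. It does not supply a baseline floor: a user at 5 mg or less meets endpoint g's condition as it stands.

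A reader might further conclude that the analysis of change in prednisone is broken because percent change is undefined from zero. That goes too far. The planned mixed model for aim 7 can use the dose itself. The difficulty is confined to endpoint f's label and the fallback analysis, and arises only if non-users can enter.

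Finally, this is one of twelve listed secondary endpoints, none with stated power, and restriction would not make an effect reliably detectable. That stands, and it limits how much weight the point can bear.

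**Conclusion.** The point holds as an inconsistency and a gap in definition. Endpoint g has a restriction that aim 8 and item 6 lack, and no version deals with patients at or below 5 mg at baseline, although entry permits them. Followed as written, item 6 would shrink the arm difference to (1 − f) of its size: 30 points becomes 24, 20 or 15 at f = 20%, 33% or 50%. Those shares and rates are assumptions. If nobody enters at or below 5 mg, there is no dilution.

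The documents do not support saying that dilution is certain, or that this wording alone would hide a real effect. In the 20% v 50% illustration, power is only 0.40 with no dilution at all. What restriction buys is an interpretable estimate, with no loss of approximate power in any case computed here. The primary endpoint and the sample size are unaffected. The change should be made, but the trial does not turn on it.

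**What to change.** 1. In endpoint g, aim 8 and item 6, state one denominator: patients in the planned analysis set with baseline prednisone (or equivalent) above 5 mg/day. Apply it at week 64 as well as week 40. Who belongs in the analysis set is a separate question and need not be reopened here.
2. Report the number in each arm excluded for starting at or below 5 mg, so that the reader can see f.
3. Reconcile Concurrent Medications with inclusion criterion 8 on whether patients taking no glucocorticoid can enter. Which of the two is intended is for the sponsor to say.
4. If non-users can enter, limit endpoint f and the percent-change fallback to baseline users, or express them as dose in mg/day. The mixed model for aim 7 can remain.

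The cost is a wording amendment, best made before unblinding, with no change to treatment, visits or data collection. The price is a smaller n for endpoint g: about 12, 10 or 8 per arm at f = 20%, 33% or 50%. Power for this comparison stays low with or without the change, so the result is best presented as an estimate with its confidence interval.

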Adults with refractory IIM will be enrolled. IIM is defined as Dermatomyositis (DM) or Polymyositis (PM), meeting the Bohan & Peter (1975) diagnostic criteria for definite or probable DM or PM. Refractory IIM is defined as chronic active IIM with a history of inadequate response or intolerance to three months of glucocorticoids and/or at least a history of inadequate response or intolerance to three months of one other immunosuppressive agent (IS) (azathioprine, methotrexate, mycophenolate mofetil, leflunomide, tacrolimus, cyclosporine, cyclophosphamide, Rituximab or intravenous gamma globulin [IVIG]).

Study Objectives:

[figure not shown]
- a. To compare the clinical response rates in refractory IIM patients on stable background treatment receiving monthly intravenous (IV) belimumab to patients receiving placebo.
- b. To assess the safety of monthly IV belimumab in patients with IIM.
- c. To evaluate the steroid-sparing effect of monthly IV belimumab added to background treatment of IIM.
- d. To evaluate the biologic effects of belimumab treatment on various B cell populations and inflammatory cytokine levels.

Study Design:

This is a multicenter randomized double-blind placebo controlled trial to evaluate the efficacy and safety of Belimumab as a maintenance therapy in adults with refractory idiopathic inflammatory myositis (IIM).

The Northwell Health Department of Rheumatology will be the coordinating site for this multi-center clinical trial. We plan to enroll 30 patients into the trial. Enrollment is competitive. Study enrollment will be carried out for two years and each patient will be followed for a total of 84 weeks.

Figure 1. Study Flowchart-overview (please check Study Schedule, Appendix A for details).

At point A, a loading dose of Belimumab will be given at week 2.

At point B, a loading dose of Placebo (saline) will be given at week 2.

a. Study Procedures and Schedule:

A simplified flowchart of the study procedure is given in Figure 1.

After consent, a patient will be randomized to either Belimumab+ standard of care (B) or Placebo+ standard of care (P). Randomization will be according to the two important stratification variables, namely, disease type (Polymyositis vs. Dermatomyositis) and disease severity (severe vs less severe) and will occur at week 0 (first infusion). There will be two major study phases: the randomized phase of the study and the open-label phase of the study, described below.

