Screening: Once the patient signs the consent form, a screening period of up to two weeks will initiate to determine the patient's eligibility for the study, prior to entering the randomization phase. Only eligible patients will enter the randomization phase.

Randomized Phase: Monthly infusions (of either B or P) will start at week 0 and continue every four weeks until week 36 (10 months) for the “randomized” phase of the study. In addition, there will be a “loading dose” at week 2 (per drug [IND] specifications). The loading dose will consist of either Belimumab or Placebo (saline) in the B or P treatment arms, respectively.

Open Label Phase: Monthly infusions (of B) will start at week 40 and continue every four weeks until week 64 (6 months) for the “open-label” phase of the study.

A comprehensive evaluation of the patient (Physical exam and history, vital signs, AEs, CBC and metabolic panel, GGT, myoglobin, pregnancy test, urinalysis, ESR, CRP, CPK, immunoglobulins, muscle and health evaluations, physician global assessment, patient self-assessments, serum level sampling) will be conducted at weeks 0, 8, 16, 24, 32, 39-40, 52, 64. A less comprehensive set of evaluations (vital signs, AEs, CBC and metabolic panel, GGT, pregnancy test) will be conducted at weeks 2, 4, 12, 20, 28, 36, 40, 44, 48, 56, 60. A detailed schedule of visits and procedures is outlined in appendix A.

A telephone follow-up conversation will also be conducted at weeks 72 and 84.

Optional Exploratory Studies

Blood based biomarker assessments and blood based RNA assessments will be performed on stored samples for consenting patients at Northwell Health only. See Appendix A (schedule of events).

b. Randomization:

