There will be no formal interim analyses or formal statistical stopping rules. However, statistical summaries of adverse event rates using 95% exact confidence intervals will be provided to the data safety monitoring board as need. During regular bi-annual meetings the data safety monitoring board will evaluate the overall rate of adverse events and unanticipated problems. Upon review the group will determine whether there are any changes needed to the anticipated benefit-to-risk assessment and if the study should continue. The results of these regular meetings will be recorded and disseminated to the other participating clinical sites. Safety data will be collected in the form of adverse events (AEs), serious AEs (SAEs) and laboratory parameters (e.g., hematology, chemistry, etc.). AEs will be recorded with the date of onset, severity, relationship to study drug, and disposition. AEs will be translated into a standard classification system such as COSTART or MedDRA. AE data will be summarized according to incidence rates, by treatment arm and by whether or not the AE was treatment related. AEs will be summarized using descriptive statistics and tabulated according to treatment group for each strata. The AE report will be descriptive, rather than inferential.

SAMPLE SIZE CONSIDERATIONS

We plan to enroll 30 evaluable patients with 15 in each of two treatment arms [B vs. P].

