- c) All events of ALT \geq 3xULN (without elevated CPK, and/or myoglobin) **and** bilirubin \geq 2xULN ($>35\%$ direct bilirubin) or ALT \geq 3xULN **and** INR >1.5 , if INR measured which may indicate severe liver injury (possible 'Hy's Law'), **must be reported as an SAE (excluding studies of hepatic impairment or cirrhosis)**; INR measurement is not required and the threshold value stated will not apply to subjects receiving anticoagulants
- d) New or worsening symptoms believed to be related to liver injury (such as fatigue, nausea, vomiting, right upper quadrant pain or tenderness, or jaundice) or believed to be related to hypersensitivity (such as fever, rash or eosinophilia)

Required Actions and Follow up Assessments following ANY Liver Stopping Event

Actions:

- Immediately discontinue study treatment
- Report the event to GSK within 24 hours
- Complete the liver event CRF and complete SAE data collection tool if the event also meets the criteria for an SAE
 - All events of ALT \geq 3xULN (without elevated CPK, and/or myoglobin) **and elevated GGT \geq 3xULN or**
 - All events of ALT \geq 3xULN (without elevated CPK, and/or myoglobin) **and bilirubin \geq 2xULN ($>35\%$ direct bilirubin) or**
 - All events of ALT \geq 3xULN (without elevated CPK, and/or myoglobin) **and INR >1.5** , if INR measured which may indicate severe liver injury (possible 'Hy's Law'), must be reported as an SAE (excluding studies of hepatic impairment or cirrhosis); INR measurement is not required and the threshold value stated will not apply to subjects receiving anticoagulants)
- Perform liver event follow up assessments
- Monitor the subject until liver chemistries resolve, stabilize, or return to within baseline (see MONITORING below)
- Do not restart/rechallenge subject with study treatment unless allowed per protocol and GSK Medical Governance approval is granted

MONITORING:

For bilirubin or INR criteria:

- Repeat liver chemistries (include ALT, AST, GGT, alkaline phosphatase, bilirubin) and perform liver event follow up assessments within **24 hrs**
- Monitor subjects twice weekly until liver chemistries resolve, stabilize or return to within baseline
- A specialist or hepatology consultation is recommended

For All other criteria:

- Repeat liver chemistries (include ALT, AST, GGT, alkaline phosphatase, bilirubin) and perform liver event follow up assessments within 24-72 hrs

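### No safety set is named, so the five-infusion inclusion rule, read as written, also drops dosed early stoppers from the only specified between-arm SAE/AE test (aim 11)

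*Combined protocol and SAP*

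**What the plan says.** STATISTICAL METHODS commits to intention-to-treat for all subjects, then says a subject is "included in the intention-to-treat analysis if he/she received at least the first five of the planned infusions" of the randomised phase. Anyone with fewer is classed as a drop-out. The seven numbered analyses follow under this rule.

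Item 7 covers specific aim 11. It is a chi-square or Fisher test "to compare the proportion of subjects who experienced any SAEs or AEs during the randomized phase of the study", with each subject classified at the end of 40 weeks as having had an event or not. It states no analysis set of its own. The only other set in the section is a secondary per-protocol analysis.

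SAFETY DATA adds descriptive reporting: "AE data will be summarized according to incidence rates, by treatment arm and by whether or not the AE was treatment related". It promises exact 95% confidence intervals to the monitoring board as needed, and says that at its regular meetings "the data safety monitoring board will evaluate the overall rate of adverse events and unanticipated problems". It attaches no infusion condition to any of this, names no denominator, and calls the AE report descriptive rather than inferential.

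**The concern.** Safety is study objective b and a secondary endpoint. A rule that admits patients only after about 12 weeks of dosing selects on something that happens after treatment starts and that toxicity can cause. An early serious event that ends treatment would take the patient out of both numerator and denominator.

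The protocol has three routes by which toxicity can end dosing before week 12, each limited:

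- **Liver stopping event (Appendix C).** Dosing stops at once, and sites are told: "Do not restart/rechallenge subject with study treatment unless allowed per protocol and GSK Medical Governance approval is granted". The protocol also says earlier lupus studies showed no causal liver link. Not every such event is an SAE: "Complete the liver event CRF and complete SAE data collection tool if the event also meets the criteria for an SAE".
- **Low IgG with severe or serious infection (Study Design, part f).** This applies after prior B-cell therapy or cyclophosphamide, and is narrowed by exclusion criteria 4, 6 and 7.
- **Serious infusion reaction (Study Drug Administration, items 2 and 3).** Infusion reactions are described as more frequent on the first two infusion days, inside the window. Permanent withdrawal is not expressly required, so this counts only if the patient is not dosed again.

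What is at stake is whether the aim 11 proportions describe everyone exposed or only those who tolerated the first five infusions.

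**Working it through.** **Where the fifth infusion falls.** Infusions run every four weeks from week 0 to week 36, plus a loading dose at week 2: weeks 0, 2, 4, 8, 12, 16, 20, 24, 28, 32, 36. The fifth is at week 12. If the loading dose were not counted it would be week 16, and the exclusion wider.

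**The plan's own figures.** The plan gives no SAE, AE or early-stop rate, so it has no aim 11 figure to reproduce. Its size for the primary endpoint (5% vs 50%, two-sided 0.05, 80% power) does reproduce at 15 per group with the pooled chi-square formula without continuity correction. I use that 15 as the number dosed per arm.

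**Assumed inputs.** 15 dosed per arm; early stoppers not replaced; bB and bP patients per arm with an SAE who pass the five-infusion rule (background); kB and kP early stoppers per arm, each with an SAE.

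**Formulas.**
- All dosed: (bB + kB)/15 − (bP + kP)/15
- Five-infusion set: bB/(15 − kB) − bP/(15 − kP)

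**Equal background, 2 per arm (belimumab vs placebo).**

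| Early SAE stops | All dosed | Five-infusion set |
|---|---|---|
| 1 vs 0 | 3/15 − 2/15 = +6.7 points | 2/14 − 2/15 = +1.0 |
| 2 vs 0 | 4/15 − 2/15 = +13.3 | 2/13 − 2/15 = +2.1 |
| 3 vs 0 | 5/15 − 2/15 = +20.0 | 2/12 − 2/15 = +3.3 |
| 0 vs 1 | 2/15 − 3/15 = −6.7 | 2/15 − 2/14 = −1.0 |
| 1 vs 1 | 0 (20.0% each) | 0 (14.3% each) |

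With 1 or 3 background patients per arm, the 1 vs 0 five-infusion difference is +0.5 or +1.4, against +6.7 in all dosed.

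**Unequal background.** The direction is no longer fixed:
- Background 4 vs 1, one stop each: 5/15 − 2/15 = +20.0 becomes 4/14 − 1/14 = +21.4.
- Background 4 vs 2, stops 0 vs 1: 4/15 − 3/15 = +6.7 becomes 4/15 − 2/14 = +12.4.

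**Stops without an SAE.** One belimumab stop with no SAE moves that arm up, from 2/15 (13.3%) to 2/14 (14.3%). Understatement therefore needs early stoppers to have more events than the rest.

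**Any AE.** If 12 of 15 have an AE (80.0%), removing one early stopper with an AE gives 11/14 (78.6%) and removing two gives 10/13 (76.9%). Common events move less.

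**Significance (two-sided Fisher).** In every row of the table p is at least 0.39 in all dosed and 1.0 in the five-infusion set. A change of call needs something like 6/15 vs 0/15 (p = 0.017). Dropping three belimumab early stoppers with an SAE makes it 3/12 vs 0/15 (p = 0.075). With one or two dropped it stays below 0.05 (5/14 vs 0/15, p = 0.017; 4/13 vs 0/15, p = 0.035).

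**The case against.** The strongest reply is that the plan is ambiguous here and does not state an exclusion. The five-infusion sentence never mentions safety, item 7 speaks of each subject, AEs are collected from the start of treatment, and SAFETY DATA has its own heading with no infusion condition. An analyst could run aim 11 on all dosed patients and claim consistency with the text. This stands as a limit on confidence. But aim 11 is on the list that the rule heads, item 7 does not lift the rule, and item 4 shows that the authors name a different subset when they want one.

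Second, the test carries little weight in a 30-patient trial whose AE report is meant to be descriptive. That is fair, and it caps the severity. Item 7 is still the only between-arm safety test specified; the multivariable models are optional and the per-protocol set would not restore early stoppers.

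Third, the root is the inclusion rule itself, and correcting it to all randomised patients would return early stoppers to aim 11. True, but a safety set would still not be named.

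Fourth, the sizes are all assumed. The denominators of 14 and 13 also assume no replacement. Study Design says "We plan to enroll 30 patients into the trial", while SAMPLE SIZE CONSIDERATIONS speaks of 30 evaluable, which could mean 15 per arm after drop-outs. This stands, and the figures are illustrations only.

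**Conclusion.** The point holds on a literal reading and is worth fixing; confidence is medium because the sentence does not mention safety. Followed as written, the plan reports aim 11 only in patients who reached the week 12 infusion. This understates an arm's rate when its early stoppers have more events than the rest. At 15 per arm each patient is 6.7 points, so one unbalanced early SAE stop can take most of a difference out of the reported estimate (+6.7 to +1.0 under the equal-background assumption).

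Four stronger readings are not supported:

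- *The rule always hides a belimumab harm.* The shrinkage in the table comes from assuming equal background counts; with unequal counts the difference can widen, and the documents give no rates.
- *It would overturn a significance result.* That happens only in extreme assumed tables, such as a 40% SAE rate against none with half of those patients stopping early.
- *Early toxicity is lost or patients are less protected.* AEs are collected from first treatment, SAEs go to the coordinating site within 24 hours, and the board summaries and descriptive tables are not tied to the rule.
- *Placebo patients' open-label belimumab contaminates aim 11.* The aim is confined to the randomised phase. Only the SAFETY DATA tables leave the phase unstated.

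**What to change.** Add to item 7 and to SAFETY DATA: *The aim 11 comparison and the randomised-phase by-arm AE tables include every randomised patient who received any amount of study agent, by treatment received; the five-infusion criterion does not apply to safety.*

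As a secondary clarification for the SAFETY DATA tables only, state that AEs from the open-label phase are tabulated separately, since placebo patients receive belimumab from week 40.

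The cost is wording; the data are already collected. The downside is that the safety denominator may differ from the efficacy denominator, which the report should state. The change should be made before unblinding.
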